5.9 Protocol Deviations

AbbVie does not allow intentional/prospective deviations from the protocol except when necessary to eliminate an immediate hazard to study subjects. The investigator is responsible for complying with all protocol requirements, written instructions, and applicable laws regarding protocol deviations. If a protocol deviation occurs (or is identified, including those that may be due to the COVID-19 pandemic), the investigator is responsible for notifying IEC/IRB, regulatory authorities (as applicable), and AbbVie.

5.10 Data Monitoring and Glucocorticoid Adjudication Committees

An external DMC will be established to safeguard the interest of trial subjects by assessing the safety of the interventions during the trial and well as for the monitoring the integrity and interpretability of the trial. A separate DMC charter will be prepared outside of the protocol and will describe the roles and responsibilities of the DMC members, frequency of data reviews, and expectations for blinded communications.

An independent glucocorticoid adjudication committee will be established to adjudicate systemic glucocorticoid AEs. A separate charter will be prepared, outside of the protocol, and will describe the roles and responsibilities of the adjudication committee members, frequency of data reviews, and expectations for blinded communications.

6 SAFETY CONSIDERATIONS

6.1 Complaints and Adverse Events

Complaints

A complaint is any written, electronic, or oral communication that alleges deficiencies related to the physical characteristics, identity, quality, purity, potency, durability, reliability, safety, effectiveness, or performance of a product/device. Complaints associated with any component of this investigational product must be reported to AbbVie.

Product Complaint

A product complaint is any complaint related to the biologic or drug component of the product or to the medical device component(s).

For a product this may include, but is not limited to, damaged/broken product or packaging, product appearance whose color/markings do not match the labeling, labeling discrepancies/inadequacies in the labeling/instructions (e.g., printing illegible), missing components/product, device damage or not working properly, or packaging issues.

Product complaints concerning the investigational product and/or device must be reported to AbbVie within 24 hours of the study site's knowledge of the event. Product complaints occurring during the study will be followed up to a satisfactory conclusion.

Medical Complaints/Adverse Events and Serious Adverse Events

An AE is defined as any untoward medical occurrence in a subject or clinical investigation subject administered a pharmaceutical product and which does not necessarily have a causal relationship with this treatment. An AE can therefore be any unfavorable and unintended sign (including an abnormal laboratory finding), symptom, or disease temporally associated with the use of a medicinal (investigational) product, whether or not the event is considered causally related to the use of the product.

Such an event can result from use of the drug as stipulated in the protocol or labeling, as well as from "special situations" such as accidental or intentional overdose, medication error, occupational or accidental exposure, off-label use, drug abuse, drug misuse, or drug withdrawal, all which must be reported whether associated with an AE or not. Any worsening of a pre-existing condition or illness is considered an AE. Worsening in severity of a reported AE should be reported as a new AE. Laboratory abnormalities and changes in vital signs are considered to be AEs only if they result in discontinuation from the study, necessitate therapeutic medical intervention, meets protocol-specific criteria (see Section 6.2 regarding toxicity management), and/or if the investigator considers them to be AEs.

The investigators will monitor each subject for clinical and laboratory evidence of AEs on a routine basis throughout the study. All AEs will be followed to a satisfactory conclusion.

An elective surgery/procedure scheduled to occur during a study will not be considered an AE if the surgery/procedure is being performed for a pre-existing condition and/or the surgery/procedure has been pre-planned prior to study entry. However, if the pre-existing condition deteriorates unexpectedly during the study (e.g., surgery performed earlier than planned), then the deterioration of the condition for which the elective surgery/procedure is being done will be considered an AE.

If any of the following events are reported, then the following supplemental report must be completed.

Event	Supplemental Report
Cardiac events Myocardial infarction or unstable angina Heart failure Cerebral vascular accident and transient ischemic attack Cardiovascular procedures (SAE Supplemental Procedure eCRF)	MACE eCRF
Discontinuation or interruption of study drug due to a hepatic-related AE A hepatic-related SAE ALT/AST > 8 × ULN or ALT/AST > 3 × ULN with a total bilirubin > 2 × ULN	Hepatic eCRF
Renal impairment Renal dysfunction Renal failure Serum creatinine >1.5 x the Baseline value and >ULN	Renal eCRF
Adrenal insufficiency	Adrenal insufficiency eCRF
COVID-19 infection	COVID-19 eCRF

AE = adverse event; ALT = alanine aminotransferase; AST = aspartate transaminase; eCRF = electronic case report form; COVID-19 = coronavirus pandemic 2019; MACE = major adverse cardiac event; SAE = serious adverse event; ULN = upper limit of normal

If an AE, whether associated with study drug or not, meets any of the following criteria, it is to be reported to AbbVie clinical pharmacovigilance or contract research organization (as appropriate) as a SAE within 24 hours of the site being made aware of the SAE (refer to Section 4.2 of the Operations Manual [[Appendix G](#)] for reporting details and contact information):

Death of Subject	An event that results in the death of a subject.
Life-Threatening	An event that, in the opinion of the investigator, would have resulted in immediate fatality if medical intervention had not been taken. This does not include an event that would have been fatal if it had occurred in a more severe form.
Hospitalization or Prolongation of Hospitalization	An event that results in an admission to the hospital for any length of time or prolongs the subject's hospital stay. This does not include an emergency room visit or admission to an outpatient facility.
Congenital Anomaly	An anomaly detected at or after birth, or any anomaly that results in fetal loss.
Persistent or Significant Disability/Incapacity	An event that results in a condition that substantially interferes with the activities of daily living of a study subject. Disability is not intended to include experiences of relatively minor medical significance such as headache, nausea, vomiting, diarrhea, influenza, and accidental trauma (e.g., sprained ankle).
Important Medical Event Requiring Medical or Surgical Intervention to Prevent Serious Outcome	An important medical event that may not be immediately life-threatening or result in death or hospitalization but based on medical judgment may jeopardize the subject and may require medical or surgical intervention to prevent any of the outcomes listed above (i.e., death of subject, life threatening, hospitalization, prolongation of hospitalization, congenital anomaly, or persistent or significant disability/incapacity). Additionally, any elective or spontaneous abortion or stillbirth is considered an important medical event. Examples of such events include allergic bronchospasm requiring intensive treatment in an emergency room or at home, blood dyscrasias or convulsions that do not result in inpatient hospitalization, or the development of drug dependency or drug abuse.

All adverse events reported from the time of study drug administration until 70 days after discontinuation of study drug administration will be collected, whether solicited or spontaneously reported by the subject. In addition, study procedure-related serious and nonserious adverse events will be collected from the time the subject signs the study-specific informed consent.

The following definitions will be used for Serious Adverse Reactions (SAR) and Suspected Unexpected Serious Adverse Reaction (SUSAR):

SAR Defined as all noxious and unintended responses to an investigation medicinal product (IMP) related to any dose administered that result in an SAE as defined above.

SUSAR Refers to individual SAE case reports from clinical trials where a causal relationship between the SAE and the IMP was suspected by either the sponsor or the investigator, is unexpected (not listed in the applicable Reference Safety Information) and meets one of the above serious criteria.

AbbVie will be responsible for SUSAR reporting for the Investigational Medicinal Product (IMP) in accordance with global and local requirements.

Adverse events will be monitored throughout the study to identify any of special interest that may indicate a trend or risk to subjects.

Safety Topics of Interest

The following safety topics of interest will be monitored during the study:

- Serious infections;
- Opportunistic infections;
- Active TB;
- Serious allergic reactions;
- Hypersensitivity reactions;
- Malignancies;
- Systemic glucocorticoid side effects;
- Adrenal insufficiency; and
- Iatrogenic Cushing's Syndrome.

Adverse Event Severity and Relationship to Study Drug

The investigator will rate the severity of each AE according to the National Cancer Institute Common Terminology Criteria for Adverse Events (NCI CTCAE Version 5.0).³

The investigator will use the following definitions to assess the relationship of the AE to the use of study drug:

Reasonable Possibility	After consideration of factors including timing of the event, biologic plausibility, clinical judgment, and potential alternative causes, there is sufficient evidence (information) to suggest a causal relationship.
No Reasonable Possibility	After consideration of factors including timing of the event, biologic plausibility, clinical judgment, and potential alternative causes, there is insufficient evidence (information) to suggest a causal relationship.

Pregnancy

While not an AE, pregnancy in a study subject must be reported to AbbVie within 24 hours of site awareness of the pregnancy. Subjects who become pregnant during the study must be discontinued (Section 5.5). If a pregnancy occurs in a study subject or in the partner of a study subject, information regarding the pregnancy and the outcome will be collected.

In the event of pregnancy occurring in a subject's partner during the study, written informed consent from the partner must be obtained prior to collection of any such information. AbbVie will provide a separate consent form for this purpose. Pregnancy in a subject's partners will be collected from the date of the first dose through 70 days following the last dose of study drug.

The pregnancy outcome of an elective or spontaneous abortion, stillbirth or congenital anomaly is considered a SAE and must be reported to AbbVie within 24 hours after the site becomes aware of the event.

6.2 Toxicity Management

The management of specific AEs and laboratory parameters are presented in Table 3. For subjects who discontinue study drug but continue study participation and are on standard of care therapies, these toxicity management requirements do not apply (including alerts from the central laboratory) and any intolerability to standard of care therapies should be managed by the prescribing physician.

Elective surgery will not be allowed during the first 24-weeks of study participation. If the subject undergoes elective surgery, study drug should be interrupted at least 2 weeks prior to the planned surgery. If the subject must undergo emergency surgery, the study drug should be interrupted at the time of the surgery. After surgery, allow reintroduction of study drug once the physician has examined the surgical site and determined that it has healed and there is no sign of infection.

Management of Hypersensitivity and Serious Allergic Reactions

Subjects should be closely monitored and assessed for the development of signs and symptoms of hypersensitivity reactions, including anaphylaxis. For any hypersensitivity reaction, appropriate therapy should be instituted per standard of care. Study drug should be discontinued if a subject develops anaphylaxis.

In the event of a suspected systemic post-dose hypersensitivity reaction, if the clinical situation allows, every effort should be made to obtain a serum sample within 2 hours but no later than 6 hours from

symptom onset for additional blood tests specified in the Operations Manual, Section 3.15 Hypersensitivity Testing.

Management of Serious Infections

Subjects should be closely monitored for the development of signs and symptoms of infection during and after treatment with study drug. Study drug should be interrupted if a subject develops a serious infection or a serious opportunistic infection. A subject who develops a new infection during treatment with study drug should undergo prompt diagnostic testing appropriate for an immunocompromised subject. As appropriate, antimicrobial therapy should be initiated, and the subject should be closely monitored. Study drug may be restarted once the infection has been successfully treated. Subjects who develop active TB must be permanently discontinued from study drug.

Management of Malignancy

Subjects who develop malignancy other than NMSC or carcinoma in-situ of the cervix must be discontinued from the study drug. Information including histopathological results should be queried for the confirmation of the diagnosis.

Management of Demyelinating Disease

Subjects must be discontinued from study drug with new onset and/or radiographic evidence of central nervous system demyelinating disease (including multiple sclerosis), optic neuritis, and peripheral demyelinating disease (including Guillain Barré syndrome).

Management of Hypertension

Subjects should be closely monitored for the development of hypertension. Investigators should consider stopping the study drug if hypertension is not successfully controlled under standard of care.

Management of Hyperglycemia

Subjects should be closely monitored for the development of hyperglycemia. Investigators should manage the hyperglycemia with appropriate standard of care.

Management of Glucocorticoid Induced Adrenal Insufficiency

Subjects should be closely monitored for signs and symptoms of adrenal insufficiency (e.g., nausea, vomiting, lightheadedness, pale skin, unexplained weight loss, low blood pressure, electrolyte abnormalities [e.g., confirmed hyponatremia < 135 mmol/L, hyperkalemia > 5.5 mmol/L], etc.) and if adrenal insufficiency is suspected, further clinical assessment and management should follow local standard of care and may include measuring of cortisol levels and/or ACTH stimulation test to be performed at a local laboratory. Glucocorticoid therapy with physiologic doses should be considered. After withdrawal of glucocorticoid therapy, adrenal insufficiency may persist for months; therefore, glucocorticoid therapy should be considered in any situation of stress (e.g., serious infection) occurring or in the months following withdrawal of study drug.

Management of COVID-19

Subjects should be closely monitored for COVID-19. Study drug should be interrupted if a subject develops a confirmed diagnosis of COVID-19. Consider the interruption of study drug in subjects with signs and/or symptoms and suspicion of COVID-19.

Management of Select Laboratory Abnormalities

For any given laboratory abnormality, the investigator should assess the subject, apply the standard of care for medical evaluation and treatment following any local guidelines. Specific toxicity management guidelines for selected abnormal laboratory values are described in [Table 3](#), and may require a supplemental eCRF to be completed (Section [6.1](#)). For subjects with ongoing laboratory abnormalities that require data entry into an eCRF, an additional eCRF related to subsequent laboratory abnormalities is only required if the subject has relevant changes in history (e.g., new onset signs or symptoms) or laboratory values that have returned to normal reference range or its Baseline value followed by subsequent laboratory abnormalities meeting toxicity guidelines (considered a new event). All abnormal laboratory tests that are considered clinically significant by the investigator will be followed to a satisfactory resolution. If a repeat test is required per the Operations Manual ([Appendix G](#)) Section 3.15, the repeat testing must occur as soon as possible.

Table 3. Specific Toxicity Management Guidelines for Abnormal Laboratory Values

Laboratory Parameter	Toxicity Management Guideline
Absolute neutrophil count	
If confirmed < 1000/μL by repeat testing with new sample, interrupt study drug dosing until ANC value returns to normal reference range or its BL value.
 
Discontinue study drug if confirmed < 500/μL by repeat testing with new sample.

Absolute lymphocyte counts	
If confirmed < 500/μL by repeat testing with new sample, interrupt study drug dosing until ALC returns to normal reference range or its BL value.

Platelet count	
If confirmed < 50,000/μL by repeat testing with new sample, interrupt study drug dosing until platelet count returns to normal reference range or its BL value.

AST or ALT	
Interrupt study drug if confirmed ALT or AST > 3 \times ULN by repeat testing with new sample and either a total bilirubin > 2 \times ULN or an international normalized ratio (INR) > 1.5.
 
A separate blood sample for INR testing will be needed to measure INR at the time of repeat testing for ALT or AST. A repeat test of INR is not needed for determination if above toxicity management criteria are met.
 
 • Interrupt study drug if confirmed ALT or AST > 3 \times ULN by repeat testing with new sample along with new appearance of fatigue, nausea, vomiting, right upper quadrant pain or tenderness, fever, rash, and/or eosinophilia (> 5% increase from Baseline). • Interrupt study drug if confirmed ALT or AST > 5 \times ULN by repeat testing with new sample for more than 2 weeks. • If ALT or AST > 8 \times ULN, interrupt study drug immediately, confirm by repeat testing with a new sample, and contact the TA MD. 
Subjects with HBc Ab+ (irrespective of HBs Ab status) or Hbs Ab+ (without a history of vaccination) and negative HBV DNA PCR testing at Screening who develop the following laboratory findings should have HBV DNA PCR testing performed within one week (based on initial elevated value):
 
 • ALT > 5 \times ULN OR • ALT or AST > 3 \times ULN if an alternative cause is not readily identified. 
 • Note: A separate blood sample for HBV DNA PCR testing will be needed at the time of repeat testing for ALT or AST. 
A positive result for HBV DNA PCR testing will require immediate interruption of study drug (unless not acceptable by local practices) and a hepatologist consultation should occur within 1 week for recommendation regarding subsequent treatment.
 
Subjects who meet any of the above criteria should be evaluated for an alternative etiology of the ALT or AST elevation and managed as medically appropriate. If applicable, the alternative etiology should be documented in the eCRF. If ALT or AST values return to the normal reference range or its Baseline value, study drug may be restarted. If restarting study drug, documentation should include reason that rechallenge is expected to be safe. If after clinically appropriate evaluation, no alternative etiology for ALT or AST elevation is found or the ALT or AST elevation has not resolved or is not trending down toward normal, the subject should be discontinued from study drug.
 
For any confirmed ALT or AST elevations > 3 ULN, complete the appropriate supplemental hepatic eCRF(s).


Laboratory Parameter	Toxicity Management Guideline
Serum Creatinine	If serum creatinine is $> 1.5 \times$ the BL value and $> \text{ULN}$, repeat the test for serum creatinine (with subject in an euvoletic state) to confirm the results. If the results of the repeat testing still meet this criterion, then interrupt study drug and re-start study drug once serum creatinine returns to $\leq 1.5 \times$ BL value and $\leq \text{ULN}$. For the above serum creatinine elevation scenario, complete the appropriate supplemental renal eCRF(s).

ALC = Absolute lymphocyte counts; ALT = alanine aminotransferase; ANC = absolute neutrophil count; AST = aspartate aminotransferase; BL = baseline; DNA = deoxyribonucleic acid; eCRF = electronic case report form; HbC Ab = Hepatitis B core antibody; HBs Ab = Hepatitis B surface antibody; HBV = hepatitis B virus; INR = international normalized ratio; PCR = polymerase chain reaction; TA MD = Therapeutic Area Medical Director; ULN = upper limit of normal

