7.5 Statistical Analyses for Safety

All safety analyses will be performed based on the Safety Population, as defined in Section 7.1. Subjects will be analyzed based on the actual treatment received. Treatment-emergent adverse events (TEAEs), laboratory assessments, and vital signs will be summarized. Key safety variables will also be summarized on the ALL_154 Population.

A TEAE for the Safety Population is defined as an AE newly occurred or worsened after the first dose of study drug and within 70 days after the last dose of study drug. The number and percentage of subjects experiencing TEAEs will be tabulated using the MedDRA system organ class and Preferred Term, by severity, and by relationship to the study drug as assessed by the investigator. Summaries (including percentages and events per 100 patient years) of SAEs, deaths, and AEs leading to discontinuation will be provided as well. Pre-treatment AEs will be summarized separately.

For selected laboratory parameters, a listing of all subjects with any laboratory value \geq Grade 3 of the Common Toxicity Criteria will be provided. Mean change in laboratory and vital signs variables will be summarized. Additional details for the safety analysis are provided in the SAP.

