Rationale: *The duration of contraception, pregnancy, and egg/sperm donation requirements after last dose of study drug was changed for the UK to align with local health authority request. The duration for each remains 70 days after the last dose of study drug administration globally, which represents greater than 5 times the upper limit of the mean elimination half-life, using the most conservative estimate of the half-life among the 3 analytes (ADC, total antibody, and payload) measured in circulation following subcutaneous administration of ABBV-154. Thus, at 70 days, no relevant systemic exposure to ABBV-154 is expected to be present.*

- Protocol Section 5.1, Eligibility Criteria: Updated criterion #24 to add "interventional" to describe clinical study type.

Rationale: *To specify that subjects cannot be enrolled in another interventional study. Noninterventional studies are permitted, as they are not expected to impact safety or efficacy of this study.*

- Protocol Section 5.1, Eligibility Criteria: For criterion #25, corrected a typographical error in the period of time to refrain from live vaccination after last dose of study drug from 12 weeks to 70 days and add clarification that 4 weeks is the minimum amount of time between receipt of a live vaccine, but duration may be longer if required locally.

Rationale: *To align with Protocol Section 5.4 and to ensure that a live vaccination is not administered during periods of relevant systemic ABBV-154 exposure, as 70 days is greater than 5 times the upper limit of the mean elimination half-life of subcutaneously administered ABBV-154.*

- Protocol Section 5.2, Contraception Recommendations: Corrected requirement #1 for Females, Non-Childbearing Potential to "Premenopausal" from "Postmenopausal." Corrected the follicle-stimulating hormone level to ≥ 30 IU/L from > 30 IU/L.

Rationale: *To correct the typographical errors.*

- Protocol Section 5.2, Contraception Recommendations: updated that both male and female condoms may be used where required by local practices in addition to the highly effective methods of birth control.

Rationale: *To clarify that where required by local practices, both male and female condoms may be used in addition to the highly effective methods of birth control which are required for all*

Females, of Childbearing Potential as either will adequately prevent the occurrence of pregnancy.

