- Protocol Section 5.7, Study Drug: Corrected time range for study drug administration to be between 7 a.m. and 11 a.m. Added sentence explaining that for LTE Period 1, the study drug (ABBV-154 or placebo) will always be administered by a healthcare/ trained professional and for LTE Period 2, study drug will be administered to all subjects by either site medical staff on-site or by the subject or designee (friend, family member, or personal health care professional), if opted for home dosing and where locally permitted.

Rationale: *To correct the typographical error for consistency with the Operations Manual. To clarify the study drug administration during both LTE Period 1 and LTE Period 2.*

- Protocol Section 6.1, Complaints and Adverse Events: Removed "AE" from the Hepatic eCRF.

Rationale: *The eCRF is applicable both for specified hepatic-related AEs and laboratory abnormalities.*

- Protocol Section 6.1, Complaints and Adverse Events: Updated wording to state that pregnancy in a study subject must be reported to AbbVie within 24 hours of site awareness.

Rationale: *To provide clarification.*

- Protocol Section 6.2, Toxicity Management: Added sentence explaining that toxicity management requirements do not apply to a subject who is discontinued from study drug but continues study participation.

Rationale: *To clarify applicability of toxicity management requirements as no ongoing risk to subject safety related to study drug is anticipated after discontinuation of study drug administration.*

- Protocol Section 6.2, Toxicity Management: Added instructions for interruption of study drug at the time of elective surgery and clarified when to re-start study drug after surgery.

Rationale: *To ensure subject safety by providing instructions for interruption of study drug related to surgery.*

- Protocol Section 6.2, Toxicity Management: Added sentence to Management of Select Laboratory Abnormalities explaining situations in which subjects with ongoing laboratory abnormalities do not require additional data entry into an eCRF.

Rationale: *To clarify and reduce duplication of eCRF data entry.*

- Protocol Appendix A, Study-Specific Abbreviations and Terms: Updated abbreviations list.

Rationale: *Added missing abbreviation for PBMC and reordered abbreviations alphabetically where needed.*

- Protocol Appendix D, List of Protocol Signatories: Updated personnel list.

Rationale: *Administrative change.*

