10.2.1 Treatment-Emergent Adverse Events

Treatment-emergent AEs are defined as any AE with the onset that is after the first dose of study drug and with an onset date no more than 5 half-lives of the study drug (i.e., 70 days). Events where the onset date is the same as the study drug start date are assumed to be treatment-emergent, unless the study drug start time and the AE start time are collected and the AE start time is prior to the study drug start time. All treatment-emergent AEs will be summarized overall, as well as by primary MedDRA SOC and Preferred Term. The SOCs will be presented in alphabetical order, and the PTs will be presented in alphabetical order within each SOC.

The number and percentage of subjects experiencing treatment-emergent AEs will be summarized.

In the ALL_154 population, treatment-emergent AEs are defined based on the first dose of ABBV-154.

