10.2.4 Treatment-Emergent Adverse Events per Patient-Years of Exposure

Exposure-adjusted AEs per 100 patient-years will be provided, where AEs per 100 patient-years of exposure are defined as the number of AEs divided by the total exposure in 100 patient-years. The study drug exposure is defined as the last dose date plus $5 \times$ half-life (70 days), minus the first dose date.

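### Protocol Section 6.2 ends central-laboratory alerts and the Table 3 ALT/AST and HBV DNA follow-up as soon as an off-drug subject is on standard of care, without waiting out the plan's own 70-day exposure window

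*Protocol*

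**What the plan says.** The exemption in Protocol Section 6.2 has three conditions: the subject is off study drug, still in the study, and on standard of care. For such subjects "these toxicity management requirements do not apply (including alerts from the central laboratory"), and intolerability to the new therapy is left to its prescriber. No time since last dose is mentioned. The reason given in Appendix F is that "no ongoing risk to subject safety related to study drug is anticipated after discontinuation of study drug administration".

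Other parts of the plan use a 70-day horizon:

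- Appendix F, explaining the contraception period: "at 70 days, no relevant systemic exposure to ABBV-154 is expected to be present".
- Protocol 6.1: adverse events from first dosing "until 70 days after discontinuation of study drug administration will be collected".
- Protocol 7.5: an event is treatment-emergent if it occurs after the first dose and "within 70 days after the last dose of study drug".
- SAP 10.2.1: treatment-emergent events are those "with an onset date no more than 5 half-lives of the study drug (i.e., 70 days").
- SAP 10.2.4: "The study drug exposure is defined as the last dose date plus" five half-lives (70 days), minus the first dose date.

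The ALT/AST row of Table 3 asks for confirmatory repeats and a search for another cause. Subjects who are HBc Ab-positive, or HBs Ab-positive without vaccination, and HBV DNA-negative at Screening "should have HBV DNA PCR testing performed within one week (based on initial elevated value") when ALT exceeds 5 x ULN, or when ALT or AST exceeds 3 x ULN without a readily identified cause. A positive result calls for a hepatologist within a week.

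**The concern.** The exemption assumes that drug-related risk ends with the last dose, while the safety analysis and the contraception rule assume that the drug can matter for another 70 days. Section 6.2 itself recognises risk after dosing: it asks for infection monitoring during and after treatment, and for adrenal precautions for months after withdrawal.

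The issue is patient safety in a small group. Section 2.2 names HBV reactivation as a rare risk of TNF antagonists. Criterion 11 admits HBc Ab-positive subjects whose HBV DNA is undetectable. Appendix E requires 12-weekly HBV testing only where local regulations demand it. For the remaining subjects, the ALT/AST-triggered PCR is the only on-study HBV check in the protocol body. The exemption can remove it while drug is still present, and just as a new csDMARD or b/tsDMARD may be starting.

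**Working it through.** **1. When the exemption can begin.** Section 5.4 has non-responders from Week 30 stop study drug and start standard of care, with no interval stated. Section 5.6 leaves treatment after any earlier stop to the investigator's judgment. The exemption can therefore begin at the stop. A subject not yet on standard of care stays covered, so the counts in step 4 are upper bounds.

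**2. What is lost.** Most Table 3 actions interrupt or discontinue study drug and are moot once it has stopped. The following are not moot: the alert, the confirmatory ALT/AST repeat, the search for another cause, the one-week HBV DNA PCR, and the one-week hepatology consultation if positive.

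**3. What continues.**

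- Investigator laboratory monitoring for adverse events (6.1).
- Assessment of abnormal results under standard of care, and follow-up of those judged clinically significant (6.2).
- Scheduled chemistry (5.6, Appendix E).
- DMC review and the study team's blinded safety review (2.2, 5.10).

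Nothing in the documents withholds results from sites. Section 5.6 waives the 30-day call and the 70-day visit for a subject with a qualifying later study visit, so these are not a guaranteed backstop for subjects who stay in the study.

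**4. Scheduled draws in the window.** The Appendix E chemistry visits are Weeks 0, 2, 4, 8, 12, 14, 18 and 24, then every 6 weeks from 30 to 78, every 8 weeks from 86 to 174, and 182. I counted draws after the last dose and up to 10 weeks (70 days) later, on nominal days, excluding the premature-discontinuation and 70-day visits.

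| Last dose or stop | Draws within 70 days | Day of first draw |
|---|---|---|
| Last dose Weeks 0-10 | 3 | 14-28 |
| Last dose Weeks 12-22 | 1-2 | 14-42 |
| Non-responder stop at Weeks 30-72 | 1 after the stop visit | 42 or 56 |
| Non-responder stop at Weeks 78-174 | 1 after the stop visit | 56 or 70 |

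Examples: a last dose at Week 4 leaves Weeks 8, 12 and 14. A stop at Week 36 leaves Week 42, which is Day 42 if the last dose was at Week 36 and Day 56 if it was at Week 34. Week 48 is then Day 84 or 98, outside the window. The paired days in the last two rows arise in this way. Appendix F records a 7-day window in LTE Period 2, so a nominal Day 70 draw can fall after Day 70, leaving none.

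**5. Drug remaining at those draws.** The SAP equates 5 half-lives with 70 days, and 70/5 = 14 days. Appendix F says 70 days is more than 5 times the upper limit of the mean half-life, so 14 days is a ceiling. The documents give no separate half-life; 10 and 7 days are my assumptions. Fraction remaining = 0.5^(t / half-life), assuming first-order decay.

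| Half-life | Day 14 | Day 28 | Day 42 | Day 56 | Day 70 |
|---|---|---|---|---|---|
| 14 days (ceiling) | 50% | 25% | 12.5% | 6.2% | 3.1% |
| 10 days (assumed) | 37.9% | 14.4% | 5.4% | 2.1% | 0.8% |
| 7 days (assumed) | 25.0% | 6.2% | 1.6% | 0.4% | 0.1% |

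Early stops therefore carry the most exposure. For a non-responder stop from Week 30, the single draw comes with at most 12.5% remaining.

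**The case against.** The exemption has a sound purpose. Once a subject takes another drug, that drug competes as the cause of an abnormal result, and its prescriber is the natural person to respond. Table 3 is presented as guidelines, and its HBV and hepatology steps are recommendations in form. The two sharpest statements, on absence of risk and on 70 days, are change-log rationales, and the latter concerns contraception and uses a conservative half-life. The 70-day adverse-event windows are data-capture conventions; none says that laboratory management must run equally long. Residual concentration is not shown to predict HBV reactivation. Harm would need a long chain: antibody-positive, no local 12-weekly testing, early start of standard of care, a raised ALT or AST at one of few draws, and an investigator who does not act.

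All of this reduces the size of the problem. It does not remove it. The rationales explain rules now in force, and the operative text in 6.1, 7.5 and the SAP uses the same 70 days. None of the continuing monitoring requires the repeat, the one-week PCR or the one-week consultation.

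Three stronger readings are tempting and are not supported:

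- **Safety surveillance stops, or sites no longer see results.** Step 3 of the working shows otherwise.
- **The hepatic eCRF for an isolated rise of 3-8 x ULN is lost.** Table 3 asks for the form above 3 x ULN. The laboratory trigger in 6.1 is above 8 x ULN, or above 3 x ULN with bilirubin above 2 x ULN. But 6.2 refers supplemental forms back to 6.1, which is not exempted, and whether a form instruction counts as toxicity management is a matter of reading. The values stay in the database, and SAP 10.3 tabulates them above 3 and 5 x ULN.
- **No other HBV provision exists.** One Appendix F rationale ties unscheduled HBV DNA visits to subjects on 12-weekly testing, but another entry says such testing may be done if necessary, without that limit. This permits testing and does not mandate it. The Operations Manual is not among the documents.

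**Conclusion.** The point holds as a cheap improvement. The exemption in 6.2 can start at the last dose, which does not fit the plan's 70-day horizon. The loss is limited to the alert, the confirmatory repeat, the search for another cause, and the one-week HBV DNA PCR with hepatology consultation if positive. It matters mainly for HBc Ab-positive (or unvaccinated HBs Ab-positive), DNA-negative subjects at sites without locally required 12-weekly HBV testing. Their number is not given and is probably small.

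On nominal days about one scheduled draw is affected for a non-responder stop from Week 30, possibly none in LTE Period 2, and up to three for a last dose at Weeks 0-10. These counts assume that standard of care starts at once. There is no effect on power, alpha, efficacy endpoints or the SAP 10.3 laboratory summaries. Confidence is medium, chiefly because the Operations Manual could not be checked.

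**What to change.** Add one sentence to Section 6.2: for central-laboratory alerts and the ALT/AST and HBV DNA steps of Table 3 (repeat test, evaluation for another cause, HBV DNA PCR, hepatology consultation), the exemption applies only from more than 70 days after the last dose of study drug. Those steps would then remain in force during the window, while treatment decisions about the standard-of-care drugs stay with their prescriber. The rest of the exemption can stand.

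The cost is the sentence and a central-laboratory alert setting; the scheduled samples are already drawn. The downside is some extra alerts and repeat tests prompted by standard-of-care drugs. Table 3 already limits the HBV part: it applies only to the antibody-positive, DNA-negative group, and where another cause is readily identified the PCR is called for only at ALT above 5 x ULN.
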